#### **8.2.1.1. Columbia-Suicide Severity Rating Scale (4 Years of Age and Older)**

Suicidality will be assessed by using the C-SSRS or, in participants with profound cognitive impairment, by the investigator's clinical judgment following interview of the participant. Where the C-SSRS is not considered appropriate and clinical interview is used instead, the reason must be clearly documented by the investigator.

The definitions of behavioral suicidal events used in this scale are based on those used in the Columbia Suicide History Form. Questions are asked on suicidal behavior, suicidal ideation, and intensity of ideation. During screening (Part A Visit 1), questions will be in relation to lifetime experiences, and all subsequent questioning will be in relation to the last assessment (since last visit).

The C-SSRS is to be completed by the investigator or his/her qualified delegate at every visit as indicated in the SoA ([Section 1.3](#)); "qualified delegate" is defined as anyone who has completed the C-SSRS training within the past 2 years or has continually administered the C-SSRS assessments throughout this study since obtaining the training certificate. The survey should be completed by the same assessor, where possible, throughout the study.

The C-SSRS will be used for participants aged 4 to 18 years (inclusive). If a participant is unable to provide adequate responses, the C-SSRS may be administered to the participant's caregiver to obtain responses on behalf of the participant.

#### **8.2.1.2. Caregiver Global Impression of Change**

The CGIC, will be performed for all participants. At screening (Part A Visit 1), the participant's caregiver will be asked to write a brief description of the participant's overall condition as a memory aid for the CGIC at subsequent visits. It is preferred that the same person performs this assessment at each visit throughout the study and should take less than 5 minutes to complete.

#### **8.2.1.3. Physician Global Impression of Change**

The PGIC will be performed for all participants and should take less than 5 minutes to complete. At screening (Part A Visit 1), the investigator will be asked to write a brief description of the participant's overall condition as a memory aid for the PGIC at subsequent visits. It is preferred that the same investigator performs this assessment at each visit throughout the study.

#### **8.2.1.4. Caregiver Global Impression of Change in Seizure Duration**

The caregiver will be asked to assess the average duration of the participant's seizures at screening (Part A Visit 1) (ie, prior to commencement of IMP) as a memory aid for subsequent visits. It is preferred that the same person performs this assessment at each visit throughout the study and should take less than 5 minutes to complete.

A series of 10 horizontal black bars of varying lengths, decreasing from left to right. The bars are positioned against a white background. The first bar is the longest, followed by a short black square, then a medium-length bar. This pattern repeats, with each subsequent bar being shorter than the previous one, creating a descending staircase effect.

### 8.2.1.9. Treatment Credibility/Expectancy Questionnaire – Parent Version

CEQ-P is a self-rated measure addressing the parents' expectancy and credibility about the treatment. CEQ-P consists of 6 items: 3 items regarding credibility and 3 items regarding expectancy. To meet the requirements of the original version of CEQ-P, items 1, 2, 3, and 5 are scored on a 9-point scale, while items 4 and 6 are scored on an 11-point scale. Items 4 and 6 are

recoded to a 9-point scale before summarizing the scales. The CEQ-P will only be administered if a translation is available in the caregiver's native language and should take 5 minutes to complete.

#### **8.2.1.10. Menstruation**

Caregivers will be asked if the female participant is menstruating, and details will be recorded as part of their randomization visit (Part A Visit 3); any changes in normal cycles will be captured at Part A Visit 9 (Day 99)/Part B Visit 1 and Part B Visit 10.

#### **8.2.1.11. Tanner Staging**

The pubic hair growth (both sexes), genital (males only), and breast (females only) development of all adolescent participants (ie, 10 to 17 years of age at the time the ICF is signed, or earlier if clinically indicated by onset of menarche or other signs of precocious puberty) will be assessed by the investigator or his/her qualified delegate using Tanner Staging ([Carel 2008](#)). The participants will undergo a discreet physical examination and be assigned a value under each category of Pubic Hair Growth (both sexes), Genitals (male participants only), and Breasts (female participants only).

Once a participant reaches a score of V (ie, 5), the examination need not be performed again.

### **8.3. Safety Assessments**

Planned time points for all safety assessments are provided in the SoA (see [Section 1.3](#)).

#### **8.3.1. Physical Examinations**

A physical examination (including height, length, head circumference, and weight) will be performed at the time points specified in the SoA (see [Section 1.3](#)).

#### **8.3.2. Vital Signs**

Vital signs will be measured in a supine position after 5 minutes rest in a quiet setting without distractions (eg, television, mobile phones) and will include body temperature, systolic and diastolic blood pressure, pulse rate, and respiratory rate. As part of screening procedures and at each clinic visit, blood pressure and pulse rate will also be taken after 2 minutes in a standing position (if it is possible for the participant to stand), following supine measurements. All measurements will be performed singly and repeated once if outside the relevant clinical reference range. Blood pressure must be recorded using the same arm throughout the study, where possible.

Additional vital signs measurements may be taken during the study, if clinically indicated.

#### **8.3.3. Electrocardiograms**

ECG will be obtained as outlined in the SoA (see [Section 1.3](#)) using an ECG machine that automatically calculates the heart rate and measures PR, QRS, QT, and corrected QT interval with Bazett correction intervals.

An ECG will be performed after 5 minutes in a supine position. A physician must review the ECG in a timely manner and any clinically significant abnormal findings considered to indicate

significant medical history or AEs must be recorded appropriately on the eCRF. Additional ECG measurements can be taken at any time during the study, if clinically indicated.

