#### Age and Sex

1. Participant must be male or female between 1 and 18 years of age, inclusive, at the time of initial informed consent/assent.
2. Participant must weigh at least 10 kg.

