### Medical Conditions

15. Has a history of psychogenic non-epileptic seizures that confounds the assessment of the primary efficacy measure.
16. Has clinically significant unstable medical condition(s), other than EMAS.
17. Has a clinically significant illness in the 28 days prior to screening (Part A Visit 1) or randomization (Part A Visit 3), other than epilepsy, which in the opinion of the investigator could affect seizure frequency.
18. Has presence of focal seizures or persistent focal epileptiform discharges on EEG.
19. Has a history of infantile spasms.
20. Has moderate to severe neurocognitive and/or developmental delay prior to seizure onset.
21. Has a progressive neurological condition.
22. Has known or suspected hypersensitivity to cannabinoids or any of the excipients of GWP42003-P such as sesame oil.
23. Is unwilling or unable to remain stable on concurrent ASMs throughout the study.
24. Has, in the opinion of the investigator, clinically significant abnormalities in the ECG measured at screening (Part A Visit 1), or any concurrent cardiovascular conditions, which will interfere with the ability to read their ECGs.
25. Has significantly impaired hepatic function at the screening visit (Part A Visit 1) or prior to dosing, defined as any of the following:
  - ALT or AST  $> 5 \times$  ULN
  - TBL (serum total bilirubin)  $> 1.5 \times$  ULN or INR  $> 1.5$ . Note that for participants diagnosed with Gilbert's disease, TBL  $> 3.0 \times$  ULN and/or direct bilirubin  $> 1 \times$  ULN are exclusionary.
  - Serum ALT or AST  $\geq 3 \times$  ULN with the presence of fatigue, nausea, vomiting, right upper quadrant pain or tenderness, fever, rash, and/or eosinophilia ( $> 5\%$ ).
  - Elevated ALT or AST at screening (Part A Visit 1), should be discussed with the medical monitor prior to randomization (Part A Visit 3); the medical monitor may allow for a confirmatory re-draw prior to randomization.

*This criterion can only be confirmed once the laboratory results are available.*

26. Has clinically significant impaired renal function at screening (Part A Visit 1), as evidenced by an estimated glomerular filtration rate (Schwartz equation)  $< 60$  mL/min.

27. Is a female participant of CBP, who is pregnant (positive pregnancy test), lactating or planning pregnancy during the course of the study and for 3 months thereafter.
28. Participant has any known or suspected history of alcohol or substance use disorder.

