#### 9.4.1. General Considerations

Unless stated otherwise, continuous data will be summarized using descriptive statistics comprising the number of participants with data to be summarized (n), mean, SD, median,

minimum (min), and maximum (max). Categorical variables will be summarized by the frequency and proportion of participants falling into each category.

For plasma concentration data and PK parameters, geometric mean, CV, and geometric CV will also be computed.

Unless stated otherwise, baseline is defined as the last record or measurement collected prior to the first dose of IMP on Day 1 (Part A Visit 3). Baseline for Part B is the same as the baseline for Part A.

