#### **9.4.5. Safety Analysis**

Safety data will be summarized using appropriate descriptive statistics.

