#### **9.4.5.4. Vital Signs, ECG, Physical Examination and Other Safety Data**

Vital signs, ECG, physical examination, and C-SSRS data will be summarized for the safety analysis set at screening, baseline, and each time point during the treatment period using appropriate descriptive statistics. Changes from baseline to each post-baseline visit will also be summarized for vital signs and ECG.

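### Bazett is the only QT correction specified for participants from 1 year of age, so QTc changes may carry a heart-rate component, mainly in uncontrolled Part B

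*Combined protocol and SAP*

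**What the plan says.** Section 8.3.3 describes a machine that "automatically calculates the heart rate and measures PR, QRS, QT" and "corrected QT interval with Bazett correction intervals". Heart rate and uncorrected QT are therefore recorded, and Bazett is the only correction named.

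On age, Section 5.1 states: "Participant must be male or female between 1 and 18 years of age, inclusive".

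ECG is listed as a secondary safety endpoint in Part A (Section 3.1) and among the primary safety endpoints in Part B (Section 3.2). Section 9.4.5 sets the general approach: "Safety data will be summarized using appropriate descriptive statistics". Section 9.4.5.4 adds: "Changes from baseline to each post-baseline visit will also be summarized for vital signs and ECG". It does not name QTc or a correction formula.

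Section 9.4.1 fixes the reference point for the extension: "Baseline for Part B is the same as the baseline for Part A". Part B is open-label with all participants on active drug, after a two-week blinded transition.

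**The concern.** Bazett divides QT by the square root of RR. If QT actually varies with RR by a smaller power, this corrects too much above 60 bpm, and by more the faster the heart. Two consequences follow. The absolute QTcB is too high in children with fast hearts. The change from baseline in QTcB also picks up any change in heart rate, on top of any real change in repolarisation.

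The second consequence matters more here, because the plan summarises changes from baseline. If heart rate fell over the study, QTcB would fall with it, which could hide some genuine prolongation. A rise in heart rate could look like prolongation. Part B is where a reader is least able to separate the two: there is no concurrent placebo arm, and the last on-treatment ECG is compared with a value taken before the first dose in Part A.

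**Working it through.** The documents state no QTc value, QTc limit or heart rate, so there is no plan figure to reproduce. What follows is an illustration.

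**From the documents:** Bazett only, with QT and heart rate recorded (8.3.3); ages 1 to 18 (5.1); changes from baseline summarised (9.4.5.4); Part A baseline kept for Part B (9.4.1); 14 weeks of treatment in Part A and 48 in Part B, so 14 + 48 = 62 weeks to the Part B end-of-treatment ECG.

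**Assumed:** heart rates of 60 to 140 bpm; a rate-independent QTc of 400 ms; a true QT-RR exponent *a* between 1/3 (Fridericia exact) and 1/2 (Bazett exact).

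**Formula.** With RR = 60/HR and QT = 400 × RR^a,

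QTcB = QT / RR^(1/2) = 400 × (HR/60)^(1/2 − a).

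At a = 1/3 the multiplier is (HR/60)^(1/6).

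**Step 1: level of QTcB at a = 1/3.**

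| HR (bpm) | QTcB (ms) | Excess over 400 ms |
|---|---|---|
| 60 | 400.0 | 0% |
| 80 | 419.6 | 4.9% |
| 100 | 435.5 | 8.9% |
| 120 | 449.0 | 12.2% |
| 140 | 460.7 | 15.2% |

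**Step 2: change in QTcB from heart rate alone at a = 1/3.** From 100 to 90 bpm: 428.0 − 435.5, which is −7.6 ms before rounding. From 100 to 80 bpm: −15.9 ms. From 100 to 110 bpm: +7.0 ms.

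**Step 3: dependence on the exponent.**

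| True exponent | Excess at 100 bpm (ms) | Shift, 100 to 90 bpm (ms) | Shift, 100 to 110 bpm (ms) |
|---|---|---|---|
| 1/3 | 35.5 | −7.6 | +7.0 |
| 0.40 | 21.0 | −4.4 | +4.0 |
| 0.45 | 10.3 | −2.2 | +2.0 |
| 0.50 | 0 | 0 | 0 |

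**Step 4: how much could be masked at a = 1/3.** If heart rate falls from 100 to 90 bpm, QTcB stays at 435.5 ms when the rate-independent QTc rises to 435.5 / (90/60)^(1/6) = 435.5 / 1.0699 = 407.1 ms. A true increase of about 7 ms would show as no change.

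**Step 5: response to repolarisation at a = 1/3 and constant heart rate.** A true +10 ms change appears in QTcB as +10.5 ms at 80 bpm, +10.9 ms at 100 bpm and +11.2 ms at 120 bpm.

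**Step 6: Fridericia is not exact either.** If the true exponent were 1/2, then QTcF = 400 / (HR/60)^(1/6). That is 400 / 1.0889 = 367.4 ms at 100 bpm and 400 / 1.0699 = 373.9 ms at 90 bpm, a spurious +6.5 ms. Above 60 bpm, with an exponent between 1/3 and 1/2, the rate-independent value lies between QTcF and QTcB.

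**The case against.** The case against has several good parts.

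- **Equipment or analysis.** Section 8.3.3 describes what the machine outputs. Section 9.4.5.4 names no correction, and Sections 9.4 and 9.4.6 defer detail to a SAP whose text is not in the combined document as supplied. A second correction may be specified there. This stands as a limit, but as written Bazett is the only QTc the plan produces.
- **Heart rates are assumed.** The documents give none, and the age range runs to 18 years. Section 2.3 lists somnolence and sedation as side effects but says nothing about heart rate. This stands, so the size can only be given as a range.
- **The exponent is assumed.** Nothing in the documents shows that the cube-root relation holds in these children, and the effect vanishes at 1/2. This stands, and argues for showing both corrections rather than replacing one with the other.
- **Part A is controlled.** With 1:1 randomisation to placebo, heart-rate drift common to both arms is offset in the comparison. Distortion there needs heart rate to change differently by arm. This stands.
- **Drift would be visible.** Heart rate comes from the ECG, pulse rate is a vital sign (8.3.2), and changes in both sets are summarised. This stands in part: separate summaries would reveal a drift but would not show how much of a QTc change it explains.
- **No decision depends on it.** ECG eligibility is a matter of judgement ("Has, in the opinion of the investigator, clinically significant abnormalities in the ECG measured at screening"). Section 7.1 has no QTc stopping rule, and QT prolongation is not an adverse event of special interest (10.4.3). This limits the importance. Even so, the Part B ECG safety reading rests on these descriptive summaries.

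A reader might infer that QTcB here tracks heart rate instead of repolarisation. It does not: step 5 shows that it responds to both, and the heart-rate part of a change is zero when heart rate is constant. A reader might also infer inflated QTc outlier counts in the youngest children. The plan states no QTc threshold or outlier table, so the documents contain no such count to inflate.

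**Conclusion.** The point holds as a conditional one of minor importance. Bazett is the only correction specified, in a population from 1 year of age. Where heart rates are well above 60 bpm and the true exponent is below 0.5, QTcB is over-corrected and its change from baseline includes a heart-rate component. At a QTc of 400 ms, a 10 bpm fall from 100 bpm contributes between 0 ms (exponent 1/2) and −7.6 ms (exponent 1/3). Heart rate, QTc level and exponent are all assumptions.

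The exposure is mainly in Part B, through the combination of no control arm, a baseline about 62 weeks before the last on-treatment ECG, and ECG as a primary safety endpoint. No sample size, error rate or numeric decision rule is affected.

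**What to change.** In Sections 8.3.3 and 9.4.5.4, prespecify QTcF, derived as QT / RR^(1/3) with RR = 60/HR from the QT and heart rate already recorded. Report its values and changes from baseline alongside QTcB and heart rate, at each ECG visit in Parts A and B. Keep QTcB, since neither formula is shown to be exact in this population; where the two disagree, heart rate in the same table helps show why. If the SAP already names a second correction, a cross-reference is enough.

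The cost is one derived variable and its summary rows. No extra ECG, visit or participant is needed.

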#### **8.3.4. Clinical Safety Laboratory Assessments**

See [Section 10.3](#) (Appendix 3) for the list of clinical laboratory tests to be performed and the SoA ([Section 1.3](#)) for the timing and frequency.

In participants with clinical risk factors for hepatocellular injury, re-assessment of laboratory safety parameters (biochemistry, coagulation, urinalysis, and hematology), including review of results should be completed up to 14 days prior to randomization (Part A Visit 3) to verify eligibility for the study. The investigator should use his/her clinical judgement along with screening assessments and consider the participant's risk factors to determine whether to re-check biochemistry and coagulation during the baseline period. Possible risk factors include but are not limited to concurrent use of valproic acid or ketogenic diet, a recent infection or illness, a history of elevated liver enzymes, elevated liver enzymes during the previous study visit, or any other relevant signs or symptoms that could indicate the participant is experiencing abnormal liver function. If re-assessment of laboratory parameters (biochemistry, hematology, urinalysis, and coagulation) is completed within 14 days of randomization (Part A Visit 3), testing at randomization (Part A Visit 3) does not need to be performed.

In the absence of clinical risk factors, per the clinical judgement of the investigator, re-assessment of laboratory parameters are not required. The laboratory results from Part A Visit 1 will serve as Part A baseline values. Part A Visit 9 laboratory results will serve as Part B baseline values.

\*Re-assessment of biochemistry and coagulation at Part A Day 57 (Visit 8) is required if there has been an adjustment to the participant's dose of IMP following Part A Day 29 (Visit 7) and/or the participant is on concurrent valproic acid and/ or participant had elevated transaminases during previous visits.

The investigator must review the laboratory report, document this review, and record any clinically significant changes (in the investigator's opinion) occurring during the study as an AE. The laboratory reports must be filed with the source documents.

All laboratory tests with values considered clinically significantly abnormal during participation in the study should be repeated until the values normalize, return to baseline, or are no longer considered clinically significant by the investigator or medical monitor or until values stabilize.

If clinically significant values do not return to normal/baseline within a period judged reasonable by the investigator, the etiology should be identified, and the sponsor notified.

All protocol-required laboratory tests, as defined in [Section 10.3](#) (Appendix 3), must be conducted in accordance with the laboratory manual and the SoA ([Section 1.3](#)).

If laboratory values from non-protocol-specified laboratory tests performed at the institution's local laboratory require a change in participant management or are considered clinically significant by the investigator (eg, SAE or AE or dose modification), then the results would be captured as AEs and appropriate follow-up actions/measures taken, if needed.

Blood sample volume requirements and processing procedures will be detailed in a separate laboratory manual; the maximum cumulative amount of blood taken in any 4-week period,

including PK blood samples, will be 2.55 mL/kg of body weight and will not exceed a total of 50 mL within any 8-week period ([Howie 2011](#)), taking into account possible repeat tests. The participant/caregiver must be advised that it may not be safe for the participant to undertake further blood tests within 1 month of any study-related blood draws and to inform the investigator if they suffered any blood loss during the 1-month period leading up to a planned blood draw.

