**Table 1: Schedule of Activities: Part A**

Study Period	Screening	Baseline Period	14-Week Dose-Optimization Treatment Period						EOT or E/W	Taper Period	Safety FU	Notes
Visit Number	1	2	3	4	5	6	7	8	9	10	11	
Week	-	-	0	1	2	3	4	8	14	16	20	
Day	-49 to -35	-28	1	8	15	22	29	57	99	110	138	
Visit Window (days)	-	-	+3	±3	±3	±3	±3	±7	±7	+3	±7	
Visit Type	Clinic	Phone	Clinic	Phone	Phone	Phone	Clinic	Clinic*	Clinic	Clinic	Phone	
Pharmacokinetics												
PK blood			X						X			Section 8.5 and Section 8.1.4
Safety and Tolerability												
CEQ-P	X											
Tanner Staging	X								X			
Menstruation question			X						X			Female participants only
CGIC	X								X			Memory aid only at Part A Visit 1
PGIC	X								X			Memory aid only at Part A Visit 1
Biochemistry & Coagulation	X		X				X	X	X			Section 8.3
Hematology	X		X				X		X			Section 8.3

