Participants will complete weekly scheduled phone visits at Day 8 (Visit 4), Day 15 (Visit 5), and Day 22 (Visit 6) and complete an in-clinic visit at Day 29 (Visit 7) and an in-clinic or home visit for review of symptoms and safety laboratory tests and to return/dispense IMP at Day 57 (Visit 8). Participants will then return to the study site for an end of treatment visit (Day 99 [Visit 9]). If a participant withdraws from the study prematurely (ie, before the end of treatment visit), an early withdrawal visit will be conducted, and a safety follow-up phone call will occur 4 weeks after their last dose of IMP. If a participant discontinues IMP prematurely, they should be encouraged to complete the end of treatment visit and the taper period and remain in the study.

Participants not continuing to Part B will return to the study site again at the end of the 10-day taper period (Day 110 [Visit 10]) and will complete a phone safety visit at the end of the follow-up period (Day 138 [Visit 11]).

Part B will be available to participants who complete Part A of the study and continue to meet all eligibility criteria and to participants for whom the investigator feels continued treatment in Part B represents a favorable risk-benefit assessment. Rollover into Part B should occur on the same day as Part A Day 99 (Visit 9).

Unscheduled phone visits can occur at any time throughout Part A, as needed.

AE, concomitant medication, and rescue medication eDiaries will be completed each day during the screening period, baseline observation period, treatment period, and taper period beginning at screening (Visit 1).

Seizure eDiaries will be completed each day during the screening period, baseline observation period, and treatment period beginning at screening (Visit 1).

IMP dosing eDiaries will be completed each day during the titration, treatment, and taper periods beginning at randomization (Visit 3).

Food eDiaries will be completed for approximately 24 hours prior to each visit where PK blood samples will be collected beginning approximately 24 hours prior to randomization (Visit 3).

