##### **9.4.5.3. Clinical Laboratory Data**

Clinical laboratory data at each visit, along with the change from baseline and percent change from baseline to each post-baseline visit will be summarized for the safety analysis set using appropriate summary statistics. Categorical shift tables will also be presented, showing the numbers of participants with values outside the normal range.

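### Part A Visit 8 (Day 57) biochemistry and coagulation are unconditional in Table 1 but conditional in Section 8.3.4, and under the conditional reading the Visit 8 laboratory summaries describe a subset selected partly after randomization

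*Combined protocol and SAP*

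**What the plan says.** **Table 1 (Section 1.3).** In "Schedule of Activities: Part A", the row "Biochemistry & Coagulation" has an X at Visits 1, 3, 7, 8 and 9. The Visit 8 X carries no condition, and the Notes cell gives only a general pointer to Section 8.3. Hematology has no X at Visit 8, so Visit 8 is a specific time point for chemistry and coagulation.

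**Adherence to the schedule.** The opening of Section 8 makes adherence to the schedule of activities mandatory. Section 8.3.4 refers to the schedule for timing and frequency, and adds that protocol-required tests "must be conducted in accordance with the laboratory manual and the SoA".

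**Section 8.3.4, condition.** A sentence that begins with an asterisk names three triggers. It opens: "Re-assessment of biochemistry and coagulation at Part A Day 57 (Visit 8) is required if there has been an adjustment". The adjustment meant is a change of IMP dose since Visit 7 (Day 29). The other two triggers are worded as follows: "the participant is on concurrent valproic acid and/ or participant had elevated transaminases during previous visits".

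**Section 4.1, Part A.** Visit 8 is described as "an in-clinic or home visit for review of symptoms and safety laboratory tests" and for return and dispensing of IMP. No subset is named, and neither are the individual tests.

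**Section 9.4.5.3.** The plan is: "Clinical laboratory data at each visit, along with the change from baseline and percent change from baseline to each post-baseline visit will be summarized". The population is the safety set, and shift tables are planned as well. The section has no rule for a visit sampled only in some participants.

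**The concern.** A site working from Table 1 draws chemistry and coagulation from everyone at Day 57. A site working from Section 8.3.4 draws them only when a trigger is present. Both would be following current protocol text.

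Two things are at stake. The first is uniform liver monitoring. Drug-induced liver injury is an adverse event of special interest (Section 10.4.3), and the liver criteria for stopping IMP in Section 7.1 rest on measured values.

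The second is how the Visit 8 laboratory summaries are read. Laboratory tests are an endpoint under the Part A objective on safety compared with placebo (Section 3.1). Two of the three triggers can arise after randomization and can depend on treatment. Titration above 10 mg/kg/day follows observed efficacy, safety and tolerability (Section 4.1), and transaminase elevation is listed among the commonly reported side effects (Section 2.3).

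**Working it through.** No figure in the plan needs reproducing. The check is a comparison of passages plus day arithmetic.

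**1. Do the documents settle which passage governs?**
- The pointer to Section 8.3 in the Notes column is general. Hematology and urinalysis carry the same one.
- Elsewhere the Notes column states a condition directly: the gene panel is marked optional, the menstruation question is limited to female participants, and the screening CGIC and PGIC are limited to a memory aid. The chemistry row has no such note.
- The reference is circular. Table 1 points to Section 8.3, and Section 8.3.4 points back to the schedule.
- The asterisk that opens the condition in Section 8.3.4 has no matching laboratory mark in Table 1. The asterisk there marks the Visit 8 visit type (clinic or home nurse).

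The text therefore does not settle it.

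**2. Interval between scheduled chemistry tests.** Inputs from Table 1: Visit 7 on Day 29 ±3, Visit 8 on Day 57 ±7, Visit 9 on Day 99 ±7.
- Table 1 reading: 57 − 29 = 28 days, then 99 − 57 = 42 days. With windows, the first interval runs from (57 − 7) − (29 + 3) = 18 to (57 + 7) − (29 − 3) = 38 days. The second runs from (99 − 7) − (57 + 7) = 28 to (99 + 7) − (57 − 7) = 56 days.
- Section 8.3.4 reading, no trigger: 99 − 29 = 70 days. With windows, from (99 − 7) − (29 + 3) = 60 to (99 + 7) − (29 − 3) = 80 days.

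**3. Which triggers fall after randomization?**
- IMP dose adjustment after Visit 7: always.
- Concurrent valproic acid: largely a baseline trait, because antiseizure medication is meant to be stable.
- Transaminases raised at previous visits: partly. Screening and pre-dose values count, but so do values at Visit 7.

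**4. Share tested and effect on the summaries.** The documents give no trigger rates, so neither can be derived. The following illustration of the mechanism uses assumed rates only. The triggers are taken as independent. Let v be the share on valproate, d the share with a dose adjustment, and e the share with an earlier elevation. Assume 60% of earlier elevations persist at Visit 8 and 3% of other participants have a new one.
- Share tested: t = 1 − (1 − v)(1 − d)(1 − e)
- Share elevated if all are tested: 0.6e + 0.03(1 − e)
- Share elevated among those tested: [0.6e + 0.03(1 − e)q] / t, with q = 1 − (1 − v)(1 − d)

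Entries are active / placebo in percent. Differences, in percentage points, are taken before rounding.

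| Assumed v; d; e | Tested | Elevated, all tested (difference) | Elevated, triggered only (difference) |
|---|---|---|---|
| 20; 20/20; 10/2 | 42/37 | 8.7/4.1 (4.6) | 16.4/6.1 (10.4) |
| 30; 30/40; 15/3 | 58/59 | 11.5/4.7 (6.8) | 17.7/5.9 (11.8) |
| 50; 50/60; 20/5 | 80/81 | 14.4/5.8 (8.5) | 17.3/6.5 (10.7) |

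Under these assumptions the Visit 8 figures shift even when the two arms are tested at nearly the same rate. The illustration gives no estimate of the size of the effect in this trial.

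**The case against.** The strongest reply is that an X in Table 1 does not mean every participant, and that Section 8.3.4 simply qualifies it. The protocol does this elsewhere. C-SSRS has an X at every visit but applies from age 4, and Tanner Staging has a plain X but applies mainly to ages 10 to 17. In the chemistry row itself, Section 8.3.4 waives the Visit 3 test if it was repeated in the previous 14 days. A footnote mark on the Visit 8 cell may also exist in the typeset table and be lost in the text version.

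This is a fair reading, and it would narrow the room for sites to differ. It would also make the triggered selection at Visit 8 part of the design. Section 9.4.1 requires the number with data to be reported, which shows the smaller denominator but does not remove the selection.

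Several stronger inferences are not supported:
- **Section 4.1 schedules these tests for everyone.** It names neither biochemistry nor coagulation, and does not say that all are sampled.
- **Practice does differ between sites.** The documents show only that it can.
- **Untriggered participants have no chemistry for 70 days.** Only scheduled tests are absent. Section 8.3.4 requires clinically significant abnormal values to be repeated, and the liver rules in Section 7.1 and Appendix 6 still apply.
- **A formal comparison is biased.** Section 9.4.5 makes the safety analysis descriptive.
- **The SAP has no rule for Visit 8.** Section 9.4 describes itself as a summary of a more detailed SAP, and no separate SAP text is in the document. Only the protocol section can be said to lack a rule.

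**Conclusion.** The inconsistency stands. Table 1 and the requirements to follow the schedule point to chemistry and coagulation at Visit 8 without condition, while Section 8.3.4 requires them only with a trigger. For a participant without a trigger, the difference is one scheduled interval of 70 days (60 to 80 with windows) against 28 and then 42 days. This rests only on the visit days and windows in Table 1.

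The consequence for analysis is conditional. If Section 8.3.4 governs, or if some sites apply it, the Visit 8 change and shift tables describe participants selected partly by dose adjustment and by transaminase elevation after baseline, and the arms can differ in that selection. A reader might infer that only a minority would be tested, or might take the illustrated percentages as estimates. The documents give no trigger rates and support neither inference.

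The effect is confined to liver monitoring and the reading of descriptive safety data at one visit. The primary efficacy analysis is untouched. The point still merits correction, because it bears on an adverse event of special interest and is cheap to resolve.

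**What to change.** Reconcile the Visit 8 entry in Table 1 with Section 8.3.4, and align the Visit 8 description in Section 4.1. Which rule governs is for the sponsor's clinical team and is not judged here. Mark the Table 1 cell to match the decision, so that the asterisked sentence in Section 8.3.4 is either tied to it or removed.

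If testing stays conditional, state in protocol Section 9.4.5.3 and in the SAP that:
- Visit 8 biochemistry and coagulation are reported separately as triggered results, with the number tested per arm;
- by-arm descriptive change and shift summaries rest on the post-baseline visits scheduled for all participants (Visits 7 and 9).

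The cost is protocol wording and, if testing stays conditional, one table footnote and a small programming change.
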